6.1.2.2 Pediatrix Administrative Database Review

Data will be extracted from the Pediatrix Medical Group Database. The following clinical and demographic variables will be included in addition to date of birth, gestation age, race, ethnicity, sex, and birth weight (Table 3).

Table 3: Variables Collected for Pediatrix Safety Study

	Date of birth	-3 days	-2 days	-1 day	On ampicillin	+1 day	+2 days	+3 days
Adverse Events (new onset)								
Cardiorespiratory arrest					X			
Hypotension					X			
Tachypnea					X			
Tachycardia					X			
Medical NEC					X			
Surgical NEC					X			
Focal intestinal perforation					X			
Grade II IVH					X			
Grade III or IV IVH					X			
Periventricular leukomalacia					X			
Cystic periventricular leukomalacia					X			
PDA requiring medical treatment					X			
PDA requiring surgical treatment					X			
Rash					X			
Seizure					X			
ROP requiring laser surgery					X			
Hyperbilirubinemia requiring exchange transfusion					X			
Laboratory Values								
AST		X	X	X	X	X	X	X
ALT		X	X	X	X	X	X	X
GGT		X	X	X	X	X	X	X
Direct bilirubin		X	X	X	X	X	X	X
WBC count		X	X	X	X	X	X	X
Neutrophil count		X	X	X	X	X	X	X
Hematocrit		X	X	X	X	X	X	X
Platelets		X	X	X	X	X	X	X
BUN		X	X	X	X	X	X	X
Creatinine		X	X	X	X	X	X	X
Glucose		X	X	X	X	X	X	X
Sodium		X	X	X	X	X	X	X
Potassium		X	X	X	X	X	X	X
Calcium		X	X	X	X	X	X	X
Magnesium		X	X	X	X	X	X	X
Phosphorus		X	X	X	X	X	X	X
Base excess		X	X	X	X	X	X	X
Positive Blood/Urine/CSF Cultures								
Organism		X	X	X	X	X	X	X
Ampicillin Dosing								
Days of administration					X			
Clinical Variables								
Mechanical ventilation					X			
Fraction of inspired oxygen					X			
Concomitant medications					X			

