10.4.2 Objective #2

Severity of diagnoses and laboratory values will be assigned according to predetermined definitions (see Appendix tables 4 and 5). A diagnosis (Appendix table 4) will be attributed to ampicillin if it was first made on a day that the infant was exposed to ampicillin. A laboratory abnormality (Appendix table 5) will be attributed to ampicillin if it occurred on a day that the infant was exposed to ampicillin or one day after exposure to ampicillin. For the cohort of patients from the PPRU Antimicrobial PK in High Risk Infants study enrolled at Reda, the frequency of diagnoses and laboratory abnormalities attributed to ampicillin will be described using standard summary statistics. For the patients exposed to ampicillin in the Pediatrix database, the frequency of diagnoses and laboratory abnormalities attributed to ampicillin will be compared to those not attributed to ampicillin. Multivariable logistic regression analyses will be performed to evaluate the association between diagnoses and laboratory abnormalities and ampicillin controlling for clinical factors associated with poor outcome in infants such as mechanical ventilation, inotropic support, and demographic features including race, gender, gestational and postnatal age. Outlier diagnostics and evaluation for multicollinearity will be performed using standard techniques. The full model containing all clinically relevant variables listed above will be compared to scaled down models using likelihood ratio tests, and the most parsimonious model that fits the data will be used for analysis. The odds of a diagnosis or laboratory abnormality occurring on a day the infant was exposed to ampicillin will be compared to the odds of occurrence on a day the infant was not exposed to ampicillin. Odds ratios and 95% confidence intervals derived from this model will be reported.

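### Laboratory abnormalities are counted on any day they occur rather than at onset, so an effect that outlasts ampicillin falls on off-drug days and the odds ratio is attenuated

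*Protocol*

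**What the plan says.** Protocol section 10.4.2 uses two counting rules. A diagnosis is attributed to ampicillin "if it was first made on a day that the infant was exposed to ampicillin". For laboratory values the rule begins: "A laboratory abnormality (Appendix table 5) will be attributed to ampicillin if it occurred on a day that the infant was exposed to ampicillin or". It then extends attribution to the following day as well. This second rule has no first-occurrence condition.

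Two analyses follow. In exposed infants, "the frequency of diagnoses and laboratory abnormalities attributed to ampicillin will be compared to those not attributed to ampicillin". The regression contrast has unexposed days as its reference: "The odds of a diagnosis or laboratory abnormality occurring on a day the infant was exposed to ampicillin will be compared to the odds of". The named covariates include mechanical ventilation, inotropic support, race, gender, gestational age and postnatal age. An earlier laboratory value is not among them.

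Section 6.1.2.2 ("Table 3: Variables Collected for Pediatrix Safety Study") carries a new-onset label on the adverse-event block but not on the laboratory block. It lists laboratory values on days -3 to -1, on ampicillin, and on days +1 to +3. Section 10.1.2 expects about 400,000 infants who received ampicillin and about 300,000 who did not. Section 10.4.2 does not say whether the second group's days enter the regression.

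**The concern.** Creatinine, transaminases, direct bilirubin and blood counts can stay beyond a Table 5 cut-off for days after they first cross it. Suppose creatinine crosses on the last ampicillin day and is still high on days +2 and +3. The single episode then gives one or two ampicillin days, depending on how day +1 is treated, and at least two non-ampicillin days. The comparison days thus contain part of the effect being looked for, in both the crude comparison and the regression.

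Section 10.4.2 also treats day +1 in two ways. The attribution sentence makes it an ampicillin day, while the odds sentence, read literally, makes it an unexposed day.

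What is at stake is the renal, hepatic and haematologic safety message. With several hundred thousand infants the intervals would be narrow, and sample size does not remove this kind of bias.

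**Working it through.** The protocol gives no effect size, onset rate or duration for Objective #2, so there is no planned figure to reproduce. The rates below are assumptions.

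**Inputs.** Assumed: off-drug daily onset h0 = 0.005; true onset ratio 2, so on-drug h1 = 0.010; probability r that an abnormality persists to the next day = 0.5, 0.7 or 0.85; 3-day course. From Table 3: three days after the course and, where they exist, three days before it.

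**Model.** Prevalence on day t is p(t) = r·p(t-1) + h·[1 - p(t-1)], with h = h1 on drug days and h0 otherwise. The steady-state start is p = h0/(1 - r + h0). The odds ratio compares the odds of mean prevalence on drug days with those on off-drug days.

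**Worked case, r = 0.7.**
- Start: 0.005/0.305 = 0.01639.
- Drug days: 0.02131, 0.02470, 0.02705; mean 0.02435.
- Days +1 to +3: 0.02380, 0.02154, 0.01997; mean 0.02177.
- Post-course reference only: (0.02435/0.97565)/(0.02177/0.97823) = 1.12.
- With three pre-course days at 0.01639, the off-drug mean is (3 × 0.01639 + 0.06531)/6 = 0.01908 and the odds ratio is 1.28.

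**All cases, steady-state start.**

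| True onset ratio | Reference days | r = 0.5 | r = 0.7 | r = 0.85 |
|---|---|---|---|---|
| 2 | +1 to +3 | 1.37 | 1.12 | 1.00 |
| 2 | -3 to -1 and +1 to +3 | 1.52 | 1.28 | 1.12 |
| 1 | either | 1.00 | 1.00 | 1.00 |

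A 7-day course gives 1.45, 1.16 and 0.98 with post-course days only, and 1.63, 1.38 and 1.17 with pre-course days added.

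**Day +1.** Moving it to the ampicillin side (3-day course) changes the first row to 1.42, 1.17 and 1.03 and the second to 1.55, 1.34 and 1.17. One carry-over day recovers little.

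**Zero prevalence at birth.** Take a course starting at birth, no pre-course days and no age adjustment. A true ratio of 2 then gives 1.17, 0.85 and 0.65. The same set-up with no drug effect gives 0.74, 0.59 and 0.49, although there is then no drug effect to carry over. Drug days simply come earlier, when prevalence is still building up from zero. Dividing one set by the other, as a rough age correction, gives 1.58, 1.44 and 1.33: attenuated, but not reversed.

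**Onset counting.** Among infants then within the cut-off, exposed against unexposed days, the odds ratio is (0.010/0.990)/(0.005/0.995) = 2.01 whatever the persistence. If day +1 is placed on the ampicillin side of a 3-day course, onset risk there averages about (3 × 0.010 + 0.005)/4 = 0.00875 and the odds ratio is about 1.76. The choice for day +1 therefore still matters after the change.

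**The case against.** A reader might infer that a harmful effect would come out as protective, since values as low as 0.65 can be produced. The documents do not support that. Those values need an unadjusted comparison, zero prevalence at birth and no pre-course days. Section 10.4.2 plans adjustment for postnatal age, Table 3 includes three pre-course days, and the protocol does not say how often a course starts at birth.

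Never-exposed infants are a second answer. If they enter at 4:3 with postnatal age as day indicators, the zero-start model with a true ratio of 2 returns about 2.0 (1.77 to 2.04 with linear age). That is a favourable case: every exposed infant is treated on the same days, so post-course days are never compared with drug days of the same age. It shows that the bias can be reduced, but the protocol does not say that these days are used. Table 3, which is laid out around a course, has no columns for them, so it cannot be read as a full list of reference days either.

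Third, the bias does not run in one direction. An abnormality already present when ampicillin starts is attributed to the drug, which pushes the odds ratio up.

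Finally, handling of repeated abnormal values could be left to a statistical analysis plan. That would carry more weight if the protocol were silent. It writes a first-occurrence rule for diagnoses and a different rule for laboratory values, and Table 3 makes the same distinction. Under the stated rules, an abnormality present on day +2 or +3 is off-drug however it began.

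**Conclusion.** The point holds as a bias from carry-over. Laboratory events lack the onset rule given to diagnoses, so days +2 and +3 of an episode that began on drug count against the reference, and the two sentences disagree on day +1. When reference days come mainly from exposed infants after their course, a true onset ratio of 2 shrinks to about 1.4, 1.1 or 1.0, or to 1.5, 1.3 or 1.1 with three pre-course days. In the least favourable of these cases the effect is lost, but it is not meaningfully reversed.

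These sizes rest on the assumed onset and persistence, a 3-day course, a steady-state start and no never-exposed infants. The net direction in the real data is not established, because abnormalities carried into a course act the other way and never-exposed infants' days could reduce the bias. The change is worth making before analysis; it does not call the design into question.

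**What to change.** In section 10.4.2:
- Define the laboratory event as onset: the first value beyond the Table 5 cut-off after a value within it, or with no earlier value.
- Assign the episode to the exposure state at onset, and remove its later days from both the exposed and unexposed risk sets until a value returns within the cut-off. This handles carry-over and, where an earlier value exists, carry-in.
- Use one rule for day +1 in both the attribution sentence and the odds sentence.
- State which off-drug days enter the regression. Take reference laboratory days from all recorded hospital days, including those of never-exposed infants at the same postnatal age, and amend Table 3 so that its window is not the limit.

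The cost is wording, programming and a wider extract of data already recorded. There will be fewer events per analyte and somewhat wider intervals.

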4 STUDY DESIGN

1) Objective #1

Prospective PK study using samples collected during the PPRU Antimicrobial Pharmacokinetics (PK) in Premature Infants Trial, POPS and Redac ampicillin PK study. The samples from the PPRU and Redac trials have been collected, labeled and tested as previously described in the individual study protocols. Analysis of these samples will be conducted by the Redac pharmacology laboratory. Samples from the POPS study are currently being collected and will be sent to the study core laboratory for analysis.

2) Objective #2

A review of all infants enrolled in the PPRU Antimicrobial Pharmacokinetics (PK) in Premature Infants Trial at Redacted will be conducted to identify the presence of safety events of interest in infants receiving ampicillin while enrolled in the PPRU study. In addition, a review of all infants in the Pediatrix Medical Group administrative database will be conducted to identify safety events occurring while on ampicillin versus when not on ampicillin.

5 Study Population

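### Days just before an ampicillin course count as ordinary reference days, so for laboratory outcomes the single odds ratio cannot separate the illness that prompted treatment from the drug.

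*Protocol*

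**What the plan says.** Protocol section 4 sets the Pediatrix review "to identify safety events occurring while on ampicillin versus when not on ampicillin". Section 10.4.2 turns this into an odds ratio with a 95% confidence interval, in which the odds on an exposed day "will be compared to the odds of occurrence on a day the infant was not exposed to ampicillin".

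The attribution rules in the same section make a timing allowance after exposure but none before it. A diagnosis is "attributed to ampicillin if it was first made on a day that the infant was exposed to ampicillin". A laboratory abnormality counts if it "occurred on a day that the infant was exposed to ampicillin or one day after exposure to ampicillin". The comparison of attributed with non-attributed frequencies is made "For the patients exposed to ampicillin in the Pediatrix database", so its comparator is the treated infants' own remaining days.

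The regression is described as "controlling for clinical factors associated with poor outcome in infants such as mechanical ventilation, inotropic support", plus race, gender, gestational age and postnatal age. No term is named for suspected infection or for closeness to the start of a course. Section 5.2 lists no exclusions for Objective #2.

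Section 6.1.2.2, under "Table 3: Variables Collected for Pediatrix Safety Study", marks laboratory values and cultures on days -3 to -1, on ampicillin, and on days +1 to +3. It marks adverse events, ventilation, inspired oxygen and concomitant medications only in the on-ampicillin column. It gives the pre-course laboratory values no separate baseline role.

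**The concern.** Section 2.1.1 presents ampicillin as treatment for sepsis, including late-onset sepsis from postnatal day 4, so some courses begin after ampicillin-free days. In such a course the days before the first dose may be those on which the infant deteriorates. Abnormal values on those days help prompt the drug, yet they are scored as events without ampicillin. The reference then mixes settled days with days of emerging illness, in a proportion that the plan does not control.

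The reported odds ratio therefore depends on that proportion and on how far the illness persists after the first dose. A reader who sees a value near or below 1 cannot tell whether the drug is harmless or the reference was already ill. A reader who sees a raised value cannot tell drug from illness. With several hundred thousand infants, sampling error may be small and such a value may look more conclusive than it is.

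**Working it through.** **No planned figure to reproduce.** The protocol gives no power, event rate or expected odds ratio for this comparison. The risks below are assumptions; the day counts come from Table 3 and the infant counts from section 10.1.2.

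**Step 1: pre-course share s of the reference days.**

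- Table 3 window only, exposed infants, laboratory values: days -3, -2, -1, +1, +2, +3. If day +1 counts as unexposed, s = 3/6 = 50%. If day +1 is attributed to ampicillin, as the laboratory rule says, s = 3/5 = 60%.
- Whole stays: assume a fraction f of 400,000 treated infants have 3 pre-course days each, and every infant has L other off-drug days. Then s = 3f × 400,000 / (3f × 400,000 + 400,000 × L). Adding the 300,000 never-exposed infants adds 300,000 × L to the denominator.
  - f = 0.1, L = 20: 120,000 / 8,120,000 = 1.5%; with never-exposed infants, 120,000 / 14,120,000 = 0.8%.
  - f = 1, L = 5: 1,200,000 / 3,200,000 = 37.5%; with never-exposed infants, 1,200,000 / 4,700,000 = 25.5%.
- A course started on the day of birth has no pre-course days and contributes nothing to s.

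**Step 2: planned odds ratio.** Reference risk = s × pre-course risk + (1 − s) × settled risk, and planned OR = odds(on-drug risk) / odds(reference risk). Assume 2% on settled days and 5% on pre-course days. The reference risk is 3.8%, 3.5% or 2.3% for s = 60%, 50% or 10%.

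| On-drug risk, and what it represents | Planned OR, s = 60% | s = 50% | s = 10% | On v settled |
|---|---|---|---|---|
| 2%: no drug effect, illness risk gone at first dose | 0.52 | 0.56 | 0.87 | 1.00 |
| 3.5%: no drug effect, half carry-over | 0.92 | 1.00 | 1.54 | 1.78 |
| 5%: no drug effect, full carry-over | 1.33 | 1.45 | 2.24 | 2.58 |
| 4%: drug doubles the risk, no carry-over | 1.05 | 1.15 | 1.77 | 2.04 |

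Example at s = 50%: (0.02/0.98) / (0.035/0.965) = 0.0204 / 0.0363 = 0.56.

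In every row, a larger pre-course share lowers the odds ratio. Down each column, a higher on-drug risk raises it, whether illness or drug is the cause.

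**Step 3: what three levels would show.** Pre-course v settled is (0.05/0.95) / (0.02/0.98) = 2.58 throughout. With no drug effect, on v pre-course is 0.39, 0.69 and 1.00 for no, half and full carry-over. The planned odds ratio of 1.00 in the half carry-over row is thereby seen to combine 1.78 against settled days with 0.69 against pre-course days.

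**Step 4: limit of that reading.** Suppose treatment lowers illness risk from 5% to 2.5% and the drug doubles it back to 5%. On v settled is 2.58, pre-course v settled is 2.58 and on v pre-course is 1.00. These equal the values for full carry-over with no drug effect, so equal odds ratios do not exclude toxicity.

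**The case against.** The strongest objection is that the planned reference may be the less biased one. Pre-course days are the off-drug days closest in illness to treated days, and an illness present the day before the first dose would not normally vanish with it. Under half carry-over at a 50% share, the planned odds ratio is exactly right (1.00), while the comparison with settled days gives 1.78. This stands. A reader might infer that the plan inflates the reference and so hides toxicity, but the documents do not determine the direction.

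A second objection is that 50% or 60% need not be the regression's share. Only the frequency comparison is expressly limited to exposed infants; sections 4 and 5.1.2 also cover infants who did not receive ampicillin. This stands too. At a 10% share, a true odds ratio of 2.04 becomes 1.77, which is attenuation and not cancellation.

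Third, Table 3 read literally marks no diagnoses before a course, so none could enter the reference. That limits the point to laboratory outcomes until Table 3 and section 10.4.2 are reconciled.

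Fourth, severity adjustment and analysis-plan detail might deal with it. The covariate list is open, but as tabulated ventilation and concomitant medications are missing for pre-course days. The protocol also does more than leave the contrast open: it fixes it.

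**Conclusion.** The point holds as a problem of interpretation. The two-level contrast places pre-course days in the reference, and no section sets them apart. Where pre-course risk is raised, this lowers the odds ratio relative to settled days. Persisting illness acts in the opposite direction, and one odds ratio cannot separate the two from a drug effect.

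The size cannot be determined from the documents. It depends on the pre-course share (50% to 60% for exposed infants within the Table 3 window; about 1% to 38% under the whole-stay assumptions above) and on carry-over, for which no data are given. With 2% and 5% risks and no drug effect, the planned odds ratio at a 50% share runs from 0.56 to 1.45. Courses started on the day of birth are unaffected.

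The point is firmest for laboratory outcomes. The documents do not support a claim that toxicity will be cancelled, or that an equally high pre-course odds ratio would clear the drug. This is an inexpensive improvement that should be made, not a fatal flaw.

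**What to change.** For laboratory outcomes in section 10.4.2, code each infant-day as pre-course (days -3 to -1 before each course), on ampicillin (with the protocol's own laboratory window), or other ampicillin-free day. Report on v other, on v pre-course and pre-course v other, beside the planned two-level odds ratio. State in advance that a raised pre-course odds ratio is evidence that confounding by indication contributes, not proof that the drug has no effect.

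State whether the regression uses the Table 3 window, whole stays or also never-exposed infants, and report the resulting pre-course share. Reconcile two places: day +1 is attributed to ampicillin for laboratory values, while the odds contrast uses exposed against unexposed days; and Table 3 marks diagnoses, ventilation and concomitant medications only on ampicillin days, while section 10.4.2 needs them on off-drug days.

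The cost is one more exposure level and a few table columns; the laboratory values for days -3 to -1 are already to be extracted. Extending the approach to diagnoses, or adjusting pre-course days for severity, would need further extraction. The downside is that the on v other odds ratio may be larger and more confounded upward than the planned one, so it must not be reported alone.

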Although ampicillin is the most commonly administered medication in the NICU, its safety in the neonatal population is poorly described. Adverse events (AE) listed on the FDA label for ampicillin are not specific to the neonatal population. Ampicillin AEs are mostly due to sensitivity phenomena that are more common in people with a history of penicillin exposure. This is very uncommon in the neonatal population. In a recent study comparing clinical efficacy of ampicillin or penicillin in combination with gentamicin therapy for early onset sepsis in infants (including GA <26 weeks), both were well tolerated with no difference in AEs or laboratory abnormalities. However, the focus of this study was clinical effectiveness comparison, and not safety profiling [15]. Among the potential serious AEs in infants is the risk of ampicillin induced seizures [4]. As with other penicillin's, β -Lactam-induced neurotoxicity is of concern if cerebrospinal fluid concentrations of ampicillin are high. This has been reported in adult case reports, but the incidence of seizures in infants, treated with ampicillin, has not been evaluated [16, 17]. Another

known side-effect of ampicillin most commonly seen after repeated dosing is inhibition of the coagulation cascade. The prevalence of this AE in the neonatal population, which is at risk of coagulopathy, is unknown [18]. Overall, given the importance of safety and improved long term outcomes in the neonatal population, a more detailed description of the safety of this commonly used antibiotic is warranted.

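### The reference days for the ampicillin odds ratio mix days on other beta-lactams with days on none, which pulls a class effect on seizure towards 1 by an unknown amount

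*Protocol*

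**What the plan says.** Section 10.4.2 defines the contrast for the Pediatrix data by infant-day. The exposed side is a day on ampicillin, and the event odds for such days "will be compared to the odds of occurrence on a day the infant was not exposed to ampicillin". It sets no condition on other antibiotics for the unexposed day. The covariates it names are "mechanical ventilation, inotropic support, and demographic features including race, gender, gestational and postnatal age", and no antibiotic is among them. It then says: "The full model containing all clinically relevant variables listed above will be compared to scaled down models using likelihood ratio tests". Section 5.2 lists no exclusions for Objective #2.

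Section 2.1.1 classes ampicillin as a beta-lactam. Section 2.1.2 names seizure as a potential serious adverse event and gives the mechanism in class terms: "As with other penicillin's, β -Lactam-induced neurotoxicity is of concern", on the condition that cerebrospinal fluid concentrations are high. It adds that seizure incidence in ampicillin-treated infants has not been evaluated. Seizure is an outcome in Table 3 and a serious diagnosis in Appendix Table 4.

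Table 3 also lists "Concomitant medications" among the variables to be extracted, but section 10.4.2 gives them no role in the model.

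**The concern.** The reference category combines two kinds of day: days with no beta-lactam, and days on a beta-lactam other than ampicillin. If the second kind carries the same neurotoxic risk, part of the effect under study sits in the comparator and cancels out of the odds ratio. This differs from confounding by drugs given together with ampicillin, and adjusting for ventilation or inotropes does not remove it.

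The direction matters in a safety study, because an odds ratio biased towards 1 reassures. Section 10.1.2 expects about 400,000 infants with ampicillin and 300,000 without, so a diluted estimate could come with a narrow interval and look settled. Sample size does not cure the dilution. Seizure is also an outcome whose incidence the protocol itself describes as a gap.

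**Working it through.** The protocol states no effect size, event rate or power for Objective #2, so there is no figure of its own to reproduce. The check is a mixture calculation.

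**Inputs**
- Reference category: any day without ampicillin (10.4.2).
- Shared effect: neurotoxicity, described as a class concern (2.1.2).
- *f*, the share of reference days on another beta-lactam: not in the document. Assumed 5% to 50%.
- OR, the true odds ratio against a beta-lactam-free day: not in the document. Assumed 1.5, 2 and 3.
- *p0*, the risk on a beta-lactam-free day: not in the document. Assumed 0.0005 and 0.01.

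**Formula.** Let *p1* be the risk on an ampicillin day, and take it to be the same on another beta-lactam day. The reference risk is (1 − f)·p0 + f·p1, and the observed odds ratio is odds(p1) divided by the odds of that mixture. For rare events this becomes

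OR_obs = OR / (1 − f + f·OR).

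For a true OR of 2:
- f = 0.10: 2 / (0.90 + 0.20) = 2 / 1.10 = 1.82
- f = 0.30: 2 / (0.70 + 0.60) = 2 / 1.30 = 1.54

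| True OR | f = 5% | 10% | 20% | 30% | 50% |
|---|---|---|---|---|---|
| 1.5 | 1.46 | 1.43 | 1.36 | 1.30 | 1.20 |
| 2.0 | 1.91 (1.905) | 1.82 | 1.67 | 1.54 | 1.33 |
| 3.0 | 2.73 | 2.50 | 2.14 | 1.88 | 1.50 |

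The baseline risk hardly matters. With the exact odds, a true OR of 2 at f = 30% gives 1.539 for p0 = 0.0005 and 1.541 for p0 = 0.01. With f = 0 the true OR is recovered in full.

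The calculation assumes an equal effect for every beta-lactam, no second beta-lactam on ampicillin days, and no confounding. It shows the direction of the bias and how the size depends on *f*. It does not estimate the bias in this database.

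**The case against.** The strongest objection concerns the remedy. Making beta-lactam-free days the sole reference would remove treated, probably infected infants from the comparator. Ampicillin is given for infection, and the named covariates include neither sepsis nor culture result. Ampicillin days would then be compared with days of infants less likely to be under treatment, which may worsen confounding by indication and push odds ratios upward. This stands, so the planned reference should not simply be replaced.

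The scope is also narrow. Section 2.1.2 states a shared effect only for neurotoxicity, and only at high cerebrospinal fluid concentrations. It mentions sensitivity reactions linked to earlier penicillin exposure but calls that very uncommon in neonates, so the support for rash is weak. That leaves firm support for one of the 17 diagnoses in Table 3. For laboratory values, the day after exposure is attributed to ampicillin, so not every ampicillin-free day is clearly a reference day. All of this stands.

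A reader might infer from the cited study "comparing clinical efficacy of ampicillin or penicillin in combination with gentamicin therapy for early onset sepsis in infants", in which "both were well tolerated with no difference in AEs or laboratory abnormalities", that penicillin days carry the toxicity in question. The protocol does not support that inference, because it adds that the study's focus was effectiveness and not a safety profile. The study shows only that penicillin can be used in the same indication.

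A reader might also infer from Table 3 that other beta-lactam days could not be recognised, since concomitant medications are marked only in the on-ampicillin column. Adverse events and mechanical ventilation are marked the same way, yet section 4 plans a review of events off ampicillin as well. The grid therefore cannot be taken as a literal limit on extraction.

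Finally, the covariates are introduced as examples, and an analysis plan could add an indicator for other beta-lactams, which would largely separate the two kinds of day. That is possible but not stated, and the full model is tied to the variables listed. Ampicillin versus no ampicillin remains a coherent contrast, but it does not isolate the class effect that section 2.1.2 raises.

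**Conclusion.** The point holds for seizure. The reference in 10.4.2 mixes two exposures that section 2.1.2 gives reason to separate, and under a harmful class effect the odds ratio is pulled towards 1. The size is unknown. The illustration of 1.82 to 1.54 for a true odds ratio of 2 rests on an assumed share of 10% to 30% and on equal effects across beta-lactams.

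Two stronger readings are tempting. One is that all the safety odds ratios are diluted, but the protocol names no shared effect for necrotizing enterocolitis, haemorrhage, ductus, retinopathy or any laboratory value. The other is that dilution is worst after severity adjustment, because sick infants' reference days are the most likely to be on another beta-lactam. That is plausible, but the protocol has no figure for it.

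**What to change.** Keep the planned ampicillin versus no-ampicillin contrast. In 10.4.2, for seizure at least and optionally for rash, add a three-level exposure for each infant-day: ampicillin; another penicillin or beta-lactam without ampicillin; neither. Use the concomitant-medication data on off-ampicillin days as well, and mark them accordingly in Table 3.

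Report two further odds ratios beside the planned one, each with its limit stated:
- **Ampicillin versus neither.** This can show a class effect but is more open to confounding by indication.
- **Ampicillin versus other beta-lactam.** This cannot show a class effect, but it compares days that are more alike in indication.

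Also report the share of reference days on another beta-lactam, so that readers can judge the possible dilution. The cost is one additional exposure definition based on a variable already listed, a little more analysis, and less precision in the split contrasts.
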